Data from the group participation will be collected and analyzed using a social media analytics tool called Grytics (https://grytics.com/). We will collect data on a weekly basis per group on the number of active members, the number of posts, the number of comments, the number of reactions to posts by type ("wow," "love," "like," "angry," "haha," and "sad"). We will also document the number and reason for personal messages to the group facilitator, such as question about side effects, question about appointment, etc. For messages, we will ask the facilitator to keep a log of messages indicating the date, time and main reason for contact.

In-depth interviews

IDIs will be conducted by trained interviewers, experienced in IDI administration, after obtaining informed consent. Once eligible participants are identified, the interviewer will contact the participant to request their participation in the interview and arrange a time to meet the participant at the health facility or another private location acceptable to the participant for the interview. The interviewer will audio-record the interview, in addition to taking notes during the interaction. The digital audio recording will then be translated and transcribed into a Microsoft Word file, which will be password protected and uploaded to the study SharePoint site for data analysis. A separate folder will be created on SharePoint with access limited to study staff within FHI 360.

A second round of IDIs will be conducted with a subset of 8-12 intervention arm participants at 12 months to explore sustainability of intervention participation.

IDIs will also be carried out with all health facility and community-based organization (CBO) staff involved in intervention coordination or implementation at the conclusion of the intervention sessions. The aim of these interviews will be to explore experiences related to intervention implementation, challenges, if any, encountered and suggestions for improving the intervention to achieve greater participation.

Cost data

Data on costs for intervention training, materials, supplies and implementation will be extracted from study financial records by study staff and entered into an Excel spreadsheet. These costs will also include facilitator stipends, CBO supervisors to facilitators and monthly meetings for facilitators. To describe relative costs of in-person support groups, data will be extracted from SIDHAS financial records.

Measures

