Cost data will include: costs associated with putting the intervention in place (training, materials, supplies, initial group meeting) and implementation (costs of cell phones, sim cards, airtime/data, facilitator stipend and staff time to purchase and distribute air time to participants).

Objective 5: To document participant engagement and perspectives regarding the content and delivery of the intervention.

Participation/engagement – For this we will record if youth participate in the components of the intervention; which components have the greatest uptake, which the least. As noted above, we will collect data on a weekly basis per group on the number of active members, the number of posts, the number of comments, the number of reactions to posts by type ("wow," "love," "like," "angry," "haha," and "sad"). We will also document the number and reason for personal messages to the group facilitator, such as question about side effects, question about appointment, etc. For messages, we will ask the facilitator to keep a log of message indicating the date, time and main reason for contact.

At the conclusion of the intervention, we will select a subset of participants for IDIs to explore their perspectives with regard to intervention content and delivery.

Objective 6: To document intervention content and fidelity by support group facilitators. At 6 months, once the intervention delivery is complete, we will analyze data from Grytics to evaluate whether facilitators were able to post push messages as outlined in the intervention guide. Timeliness and completion of each scheduled activity will be evaluated. Additionally, notes from facilitator meetings will be used to understand facilitators' experiences delivering the intervention.

Table 2. Summary of key study measures by objective.

Study objective	Concept/variable	Measures	Source of data
Objective 1; To test the	Retention in HIV	Dates of clinic visits during study	Medical record data
effectiveness of a structured online	services		
support group to retention in HIV		Questions regarding clinic visits,	Structured
services among YLHIV.		missed visits, reasons for missing	questionnaires.
		visits	
Objective 2: To examine the effect	Social support	MOS-SSS items	Structured baseline and
of the online support group on			endline participant
social support, HIV knowledge and			questionnaires
treatment literacy, and ART	ART Adherence	AACTG Adherence Assessment	Structured baseline and

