For this study, we will be implementing the full version of the online support group intervention piloted in the feasibility study and conduct a randomized controlled trial to evaluate its impact on retention in HIV care services. The intervention components include:

- Informational messages that reflect the content of the structured group counseling curriculum, • Positive Connections, and are posted to the group wall on a regular basis several times a week, for approximately 4 to 4.5 months
- Moderated, closed group chats in a "secret" Facebook group where YLHIV can interact with their peers and with a trained health counselor
- Access to a trained counselor via Facebook Messenger or phone for the duration of the intervention who will be able to provide information or basic counseling on ART/HIV care related issues, with referral to health care services as needed

Ι. Study Aim and Objectives

The principle aim of this research is to gather evidence on an intervention designed to improve retention in HIV care services among youth living with HIV, ages 15-24 years, enrolled in ART services.

The objectives of the study are:

- 1. To test the effectiveness of a structured online support group (SMART Connections) to increase retention in HIV services among YLHIV.
- 2. To examine the effect of the SMART Connections on secondary outcomes of social support, HIV knowledge and treatment literacy, and ART adherence among YLHIV.
- 3. To test the potential mediating effect of social support on the relationship between the intervention and primary outcome.
- 4. To document the costs of the intervention and calculate the unit cost per YLHIV retained. Intervention costs will also be descriptively compared to the costs of adolescent-focused, in-person support groups in the region.
- 5. To document participant engagement and perspectives regarding the content and delivery of the intervention to inform scalability and sustainability.
- 6. To document implementation and health care provider and support group facilitator perspectives regarding intervention content and delivery to inform scalability and sustainability.

The study's primary outcome is retention in HIV services at 6-9 months after enrollment. The study's secondary outcomes are:

- 1. ART adherence
- 2. Social support

3. HIV knowledge and treatment literacy

11. Study Design

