This study will be a randomized controlled trial (RCT) of the SMART Connections, a socio-behavioral intervention using an online social media platform (Facebook) designed to improve retention in HIV care services. Participants will be randomized to the online intervention group or control group (standard of care).

The hypothesis being tested with this study is:

YLHIV who participate in SMART Connections will be more likely to be retained in HIV care at 6-9 months after enrollment than YLHIV in the control group.

Secondarily, we will also test the role of social support as a potential mediator of the intervention effects on retention in care:

Among YLHIV enrolled in ART services, those in the treatment group who are exposed to SMART Connections will have greater social support and, in turn, will be more likely to be retained in HIV care services at 6-9 months compared to those in the control group.

Sample Size and Sampling Design 111.

Sample size

Our primary outcome is retention in HIV care. We will need to recruit 250 experimental participants and 250 control participants to be able to detect a 0.125 difference in the cumulative probability of retention at 12months (0.45 in the control group and 0.575 in the intervention group), corresponding to a hazard ratio of 0.69, with 80% power and 5% significance level for a two-sided comparison using the log-rank test. These calculations also assumed exponential times to event and a 10% loss to follow-up.

Sampling and recruitment procedures

Eligible participants will be sequentially recruited from patients who attend clinic visits at the study facility until the total sample size has been achieved. Potential participants will be assessed for eligibility and written informed consent will be obtained from each participant prior to enrollment in the study.

Randomization procedures

A randomization manager from FHI 360, who is not otherwise involved in the study, will prepare a computerized randomization list using permuted blocks before the start of the study. These envelopes will be given to study staff in charge of the enrollment process. These staff will open the randomization envelopes and inform the participant which group s/he has been assigned to. Participants will be randomized in a 1:1 ratio to proceed with the study procedures. The master randomization list will be maintained at FHI 360 and will not be available to study staff.

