To estimate the total costs for the intervention, we will use FHI 360's intervention costing approach to measure costs of intervention activities. FHI 360's approach classifies activities according to three distinct phases: design/development, preparation for implementation, and implementation. We will concentrate on the second and third phases, because costs of design and development activities are not repeated during scale-up. Costs associated with "preparing for implementation" include training of facilitators and other direct costs of implementation such as printing and field logistics, specifically:

- Facilitator training:
 - o Travel
 - Per diem
 - o Venue rental
 - Printed materials
 - Other training materials
 - o Refreshments
- Other non-training related or pre-implementation costs

Costs of implementation are those associated with carrying out the activity including:

- Monthly facilitator meetings
 - o Transportation reimbursement
 - Refreshments
 - Facilitator stipend
- Equipment
 - Phones for facilitators
 - Airtime/data bundles for facilitators
 - Phones for participants
 - Airtime/data bundles for participants

We will also calculate the unit cost per participant, by dividing the total cost by the number of study participants who were assigned to a Facebook group, as well as the unit cost per participant retained, by dividing the total cost by the number of study participants who were assigned to a Facebook group and were retained in HIV care at endline.

Objective 5.

Participant engagement will be summarized descriptively by session and group using data collected by the Grytics software. We will summarize the number of participants' posts and comments, as well as "likes" and other reactions ("love," "haha," "sad," etc.) to scheduled posts, by intervention session, week, and group. Participant perspectives on intervention content and delivery from structured questionnaires conducted at endline will also be summarized using descriptive analyses including means and frequencies. Qualitative

analysis of in-depth interviews with participants at endline will provide further context and detail about participants' thoughts on the intervention and its usefulness.

Objective 6.

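### The planned cost per participant retained is an average that makes no use of control-arm retention; an incremental cost per additional youth retained should stand beside it

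*SAP*

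**What the plan says.** The objective, in SAP section I, is "To document the costs of the intervention and calculate the unit cost per YLHIV retained". SAP section VI, Objective 4, defines two unit costs. One is total cost per participant assigned to a Facebook group. The other has as its denominator "the number of study participants who were assigned to a Facebook group and were retained in HIV care at endline".

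Total cost covers preparation and implementation. Design and development are left out: "We will concentrate on the second and third phases, because costs of design and development activities are not repeated during scale-up". The implementation list includes phones and airtime or data for participants. The SAP summary table classes the unit cost as descriptive.

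The only comparison planned is with another form of delivery: "Intervention costs will also be descriptively compared to the costs of adolescent-focused, in-person support groups in the region". Control-arm retention enters no cost calculation in either document, and neither plans a cost per additional youth retained.

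Endline retention is defined in SAP section IV.C by a 28-day window around the scheduled visit. The sample size in SAP section III assumes 12-month retention of "0.45 in the control group and 0.575 in the intervention group".

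**The concern.** The trial randomises 1:1 to standard of care, so it measures directly how many youth stay in care without the online group. The unit cost leaves that information out and counts everyone retained in the intervention arm as bought by the intervention.

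Two consequences follow. First, a programme that reads the figure as the price of keeping one more young person in care will take it to be much lower than it is. Second, the figure responds weakly to effectiveness and strongly to background retention, so an intervention with no effect still gets a finite and fairly similar value. The protocol's dissemination section sends the results to the funder and the service project for integration into care programmes, so this misreading is a practical risk.

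**Working it through.** **Plan's own figures.** The documents state no cost amount, so there is none to reproduce. The planning retention figures are coherent:

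- ln(0.575)/ln(0.45) = 0.693, matching the stated hazard ratio of 0.69.
- The Schoenfeld formula gives 234 events. With 10% loss treated as exponential censoring, the mean event probability is 0.4655, so N = 234/0.4655 = 503, against the planned 500.

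**Inputs.** n = 250 in the intervention arm, p1 = 0.575, p0 = 0.45 (SAP section III). C is the cost per assigned participant; its amount is unknown and it cancels from the ratio.

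**Who is in the denominator.**

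- Retained in the intervention arm: 250 × 0.575 = 143.75.
- Expected to be retained without the intervention: 250 × 0.45 = 112.5, or 112.5/143.75 = 78%.
- Additional: 250 × 0.125 = 31.25.

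**Two costs, same C in both.**

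- Average cost per retained = C/p1 = C/0.575 = 1.74C.
- Incremental cost per additional retained = C/(p1 − p0) = C/0.125 = 8.0C.
- Ratio = p1/(p1 − p0) = 0.575/0.125 = 4.6.

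**Response to a smaller effect, control held at 0.45.**

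| Difference | Average | Change from plan | Incremental | Ratio |
|---|---|---|---|---|
| 0.125 | 1.74C | – | 8.0C | 4.6 |
| 0.0625 | 1.95C | +12% | 16.0C | 8.2 |
| 0 | 2.22C | +28% | unbounded | – |

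**Other control retention (assumption).** If control retention were 0.652 to 0.85 with the same 0.125 gain, the ratio would be 6.2 to 7.8, and a null effect would raise the average by 19% to 15%.

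**Items both arms receive.** The protocol gives controls a study phone (Intervention Description), and its Compensation section does not limit phones or monthly data to one arm. If these items are a share s of C (not given), a net incremental cost is C(1 − s)/0.125, and its ratio to the SAP's full-cost average is 4.6(1 − s). This gives 3.45 at s = 0.25 and 2.3 at s = 0.5; it reaches 1 at s = 1 − 1/4.6 = 0.78.

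**Precision.** Simple normal interval, 250 per arm, full C:

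- Observed difference 0.125: SE = √(0.575×0.425/250 + 0.45×0.55/250) = 0.0444, 95% CI 0.038 to 0.212, so about 4.7C to 26C per additional youth.
- Observed difference 0.0625: SE = √(0.5125×0.4875/250 + 0.45×0.55/250) = 0.0446, 95% CI −0.025 to 0.150, so from about 6.7C with no upper limit.

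**The case against.** The strongest reply is that the SAP does what it says. Objective 4 asks for a unit cost per youth retained, section VI computes that, and the table labels it descriptive. This stands: the figure understates only a quantity that the plan never claims to estimate. The purpose of informing scalability is attached to Objectives 5 and 6; under Objective 4, scale-up appears only as the reason for excluding design costs.

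It can also be said that a reader could derive the incremental figure from the cost per assigned participant and the retention results by arm. This stands in part. The survival analysis stops at 270 days and the descriptive proportion is at 12 months, while the cost denominator uses endline status. The reader would have to mix definitions and would get no interval.

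Three stronger readings are tempting, and the documents do not support them:

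- *The denominator drops those who never joined.* The protocol's in-depth interview section describes people who opted out of joining as still assigned to a group, so assigned can mean randomised.
- *The cost list is incomplete and favours the online group over in-person groups.* The protocol requires "facilitator stipend and staff time to purchase and distribute air time to participants" under Measures, as well as the initial group meeting, and states under Cost data: "These costs will also include facilitator stipends, CBO supervisors to facilitators and monthly meetings for facilitators". SAP section IV.A also names supervisors. The list in section VI does not repeat these items, but its implementation part is not exhaustive and its preparation part has a catch-all. The in-person list names no training, supervision or staff time either, and the online side carries phones and data. No direction of bias is established.
- *The trial's ratio will be 4.6.* That holds only for the planning figures with full cost on both sides.

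**Conclusion.** The unit cost per participant retained is a valid average cost, but it cannot show what the intervention adds. On the 12-month planning figures it is 1.74C against 8.0C per additional youth retained, and it rises only 28%, to 2.22C, if there is no effect.

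The 4.6-fold gap rests on 0.575 against 0.45 and on the same C in both figures. The realised ratio will differ for two reasons. The denominator is endline status under a 28-day window, with a primary outcome that the SAP places at 6–9 months. The gap also narrows to 4.6(1 − s) if the phones and data that controls also receive are netted out, with s unknown. A reader should not infer an arithmetic error. This is a cheap and worthwhile addition that uses control-arm data the trial already collects.

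**What to change.** In SAP section VI, Objective 4:

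1. Keep the existing figure and label it an average (descriptive) cost per participant retained.
2. Add the incremental cost per additional youth retained: cost per randomised intervention participant divided by the between-arm difference in endline retention, with the same retention definition in both arms.
3. Derive its interval from the confidence interval of that difference. When that interval includes zero, report the cost interval as open-ended; do not suppress the estimate, since that would make reporting depend on a significance test.
4. Show the figure twice: with participant phones and data at full intervention cost, and net of those also given to controls. The first is nearer to what a programme would pay; the second matches the between-arm contrast.

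A cross-reference from the SAP cost list to the protocol's Cost data and Measures sections would be an optional clarification.

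The cost is some SAP wording, one further division, and the netting of control-arm phones and data. Retention is already collected in both arms. The downside is a less favourable and less precise figure.
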